3 ELIGIBILITY CRITERIA

Inclusion Criteria:

- Female subjects \geq 18 years old with ultrasound visible breast abnormalities (BI-RADS 3*, 4A, 4B, 4C, and 5) referred for ultrasound-guided core needle biopsy or fine needle aspiration
- Willing and able to provide informed consent

(*note that while a BI-RADS 3 assessment is probably benign, a subset of patients with this assessment choose to undergo biopsy rather than follow up imaging).

Exclusion Criteria:

- Lesions located in the darkly pigmented nipple-areolar complex area
- Subjects with breast implants
- Abnormality in the mirror image location of the contralateral breast.
- Additional abnormalities in the same region of the breast that would be included in US-guided DOT imaging of the abnormality undergoing biopsy
- Previous breast irradiation of the mirror image location of the contralateral breast
- Lesions located at previous biopsy sites when biopsy occurred within the last six months.
- Pregnancy
- Superficial abnormalities located entirely within (i.e. less than) 5mm of the overlying skin

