7. DATA COLLECTION AND ANALYSIS

Study specific data will be collected from subjects after informed consent is obtained. The following data may be collected on the patient questionnaire: demographic information (name, DOB, Age, Race and Hispanic or Non-Hispanic) MRN#, imaging reports (e.g. mammography, US, PET, MRI, etc.), core biopsy pathology reports, surgical pathology reports if available, breast cancer risk information, etc.

In some cases, the pathologist may review existing biopsy specimens with special staining to look for signs of increased blood supply and vessel density. This will not require additional slicing of standard of care biopsy specimens; thus, samples will not be labeled or stored for the research study. The results of these tests will not be placed in the patient medical record. The results of these tests may be given to the investigators to correlate to the results of the NIR/US procedures.

[figure not shown]
[name], specialist in breast pathology, will assess pathological findings.

The goal of this study is to assess the impact of adjunctive US-guided DOT on the accuracy of breast biopsy recommendations for abnormalities undergoing US-guided breast biopsy. In particular to assess the effect of combining US-guided DOT with CI to: 1. reduce the rate of benign breast biopsy, i.e. decrease false positive biopsy recommendations, and 2. to maintain sensitivity, i.e. maintain true positive recommendations.

Additional goals of this study are to assess the role of US-guided DOT in managing discordant biopsy results and assess the correlation of optical imaging parameters with the presence

and intensity of contrast enhancement of the abnormality undergoing biopsy in patients who have undergone CEM.

Figure 4 – Reader Study Design

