From a total of 300 patients who undergo the US-DOT exam, we expect to recruit a small subset of patients with BI-RADS 4C or 5 lesions whose biopsy results are benign. We will correlate initial biopsy results, optical data and gold standard final pathology for this subset of patients. This pilot data will allow us to assess the potential benefit of US-guided DOT in managing discordant abnormalities, i.e. reducing additional invasive procedures of a subset of benign abnormalities.

Exploratory Aim 1.4 Explore and compare US-guided DOT and CEM
In this exploratory aim, we will evaluate the agreement (Kappa coefficient) of US-guided DOT and CEM, as both modalities measure alterations in lesion vascularity. We will compare BI-RADS assessments of CI&CEM vs. CI&US-guided DOT as well as correlate imaging data such as intensity of enhancement in CEM and the total hemoglobin level of US-DOT.

Alternative plan: *If US-guided DOT is not comparable with CEM we will evaluate the capability of US-guided DOT in improving the accuracy of combined CI&CEM because CEM may become SOC in a significant subset of patients.*

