10.4 Data Analysis

All data will be analyzed as it is without imputations. Summary statistics will be used to summarize data including mean, median, standard deviation, interquartile range for continuous data and count (percentage) for categorical data.

All evaluable subjects will be analyzed. In addition to the specificity and sensitivity of US-guided DOT results, PPV, NPV, and overall accuracy will be calculated. The two study hypotheses will be tested by a binomial exact test and by constructing the one-sided 97.5% Clopper-Pearson exact confidence intervals for specificity and sensitivity. The lower limit will determine the achievement of study goals. We will explore the data further to refine the classification algorithm and the cut-off threshold. ROC analysis will evaluate the quantitatively measured tHb for pathological results of malignant biopsies. Besides tHb and its distribution, other parameters (such as oxyHb, deoxyHb, and distributions) will be either linearly incorporated with tHb to maximize the ultimate area under ROC or non-linearly through a tree-based classification model (e.g., using the R package “rpart”) (62).

The area under the ROC will be calculated to gauge the model's overall discriminative ability for biopsy results.

For the exploratory study (discordant biopsy results), the imaging data (e.g., tHb, oxyHb etc) will be summarized as appropriate in the subset of participants whose BIRAD results yield highly suspicious abnormalities (BI-RAD 4C, 5) but pathology yield benign results. Two sample t-test or Wilcoxon rank sum test as appropriate will be applied to compare this subset versus those with a malignant biopsy.

For the exploratory Study (CEM DOT correlation), we will compare BI-RADS assessments of CI&CEM vs. CI&US-guided DOT as well as correlate imaging data such as intensity of enhancement in CEM and the total hemoglobin level of US-DOT using Pearson or Spearman correlation coefficients. We will evaluate concordance/disconcordance between US-guided DOT and CEM using agreement measure (Kappa coefficient) and will test the discordance using McNemar test.

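### The exploratory DOT–CEM analyses are not split by pathology, so they can describe agreement but cannot show which modality is more accurate

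*Combined protocol and SAP*

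**What the plan says.** Section 10.4 names three analyses for the CEM subset. The first is a comparison of assessments, with no method given: "we will compare BI-RADS assessments of CI&CEM vs. CI&US-guided DOT". The second is a Pearson or Spearman correlation of enhancement intensity with tHb. The third is: "We will evaluate concordance/disconcordance between US-guided DOT and CEM using agreement measure (Kappa coefficient) and will test the discordance using McNemar test".

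Section 7.1, Exploratory Aim 1.4, repeats the comparison and the correlation and gives the reason for the kappa: "we will evaluate the agreement (Kappa coefficient) of US-guided DOT and CEM, as both modalities measure alterations in lesion vascularity". It then adds an alternative plan: "If US-guided DOT is not comparable with CEM we will evaluate the capability of US-guided DOT in improving the accuracy of combined CI&CEM". No criterion for being comparable is given.

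None of these analyses is tied to pathology. Accuracy measures are named for DOT only: "In addition to the specificity and sensitivity of US-guided DOT results, PPV, NPV, and overall accuracy will be calculated". Pathology is nevertheless available, because every enrolled lesion is "referred for ultrasound-guided core needle biopsy or fine needle aspiration", and Section 7.1 has CEM and biopsy results entered in the same database for analysis.

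**The concern.** A lesion called positive on CEM and negative on DOT counts in DOT's favour if it is benign and against DOT if it is malignant. Over all lesions, McNemar puts both in the same cell. A modality that is better in both groups calls more malignant lesions positive and fewer benign lesions positive, so its two advantages pull the overall positive rate in opposite directions. Kappa does not change if the two modalities are swapped, so it carries no information on which of them is right.

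What is at stake is the reading of the exploratory comparison. Low agreement could mean that DOT is better or that it is worse. A non-significant McNemar could conceal differences in both sensitivity and specificity. The alternative plan is about accuracy, yet nothing planned before it measures the accuracy of DOT against that of CEM.

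**Working it through.** **Plan's own figures.** No sample size, power or margin is given for the CEM aim. The nearest figures are the one-sided exact binomial powers in Section 10.3, and they reproduce:
- 83 benign, specificity 45% against 30%: reject at 34 or more, power 80.18%.
- 210 benign, same specificities: reject at 77 or more, power 99.40%.
- 90 malignant, sensitivity 98% against 90%: reject at 87 or more, power 89.33%.

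Their only use here is the expected mix of 210 benign to 90 malignant, which is 70% to 30%.

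**Assumptions.** The documents do not give the size of the CEM subset, its benign-to-malignant mix, the accuracy of CEM, the cut for CEM or a level for McNemar. I take subset sizes of 50 to 300, the trial's 70:30 mix, the cut that Section 7 gives for DOT (BI-RADS 2–3 negative, 4A–5 positive), one read per modality, and a two-sided 0.05 level.

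**Step 1: what McNemar over all lesions tests.** With prevalence π of malignancy, the difference in overall positive rate is

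π × (difference in sensitivity) − (1 − π) × (difference in specificity).

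At π = 0.30 this is zero when the sensitivity gain is 0.70/0.30 = 2.33 times the specificity gain. For gains of 28 and 12 points: 0.30 × 28 − 0.70 × 12 = 8.4 − 8.4 = 0.

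**Step 2: small example, assumed counts.** Ten benign lesions are CEM-positive and DOT-negative, six malignant lesions are CEM-negative and DOT-positive, and there are no other disagreements. DOT is right in all 16. Exact two-sided McNemar gives:
- all lesions, 10 v 6: p = 0.45
- benign, 10 v 0: 2 × 0.5^10 = 0.002
- malignant, 6 v 0: 2 × 0.5^6 = 0.03

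If the six malignant disagreements ran the other way, the overall count would be 16 v 0, with p = 2 × 0.5^16 = 0.00003. That result would combine a gain in specificity with a loss in sensitivity, so a significant overall test cannot be read as better or worse either.

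**Step 3: example at the trial's mix.** Assume 100 CEM patients, 30 malignant and 70 benign. Modality A has sensitivity 29/30 and specificity 31/70; B has 21/30 and 23/70. Both are positive in 60 lesions, A only in 8, B only in 8, and neither in 24.
- Overall McNemar, 8 v 8: p = 1.00.
- Observed agreement is 0.84 and chance agreement is 0.68² + 0.32² = 0.5648, so kappa = (0.84 − 0.5648)/(1 − 0.5648) = 0.63.
- By pathology: 8 v 0 in each group, both in favour of A, p = 2 × 0.5^8 = 0.008 each.

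Swapping the labels A and B leaves the kappa and the overall McNemar p-value unchanged.

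**Step 4: simulated rejection rates.** 5,000 replicates per scenario, with reads independent given pathology.

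| Sensitivity | Specificity | N | All lesions | Malignant only | Benign only |
|---|---|---|---|---|---|
| 98% v 70% | 45% v 33% | 50 | 2% | 23% | 12% |
| 98% v 70% | 45% v 33% | 100 | 3% | 81% | 24% |
| 98% v 70% | 45% v 33% | 150 | 3% | 96% | 39% |
| 98% v 90% | 45% v 30% | 100 | 21% | 5% | 37% |

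The first three rows sit at the cancelling ratio, and the overall test stays near 3% as the subset grows. The last row is away from it: 0.30 × 8 − 0.70 × 15 = −8.1 points. Cancellation is then partial, and neither pathology group has good power.

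**The case against.** The strongest reply is that this is an agreement aim. Section 7.1 justifies kappa by the vascularity that both modalities measure, Section 7 lists the CEM work as a correlation among its additional goals, and Section 10.4 labels it in the same way. For that question kappa and correlation are suitable, and no agreement statistic is expected to show which method is right. This stands, and it limits the point to the BI-RADS comparison and to the alternative plan.

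Four stronger readings are tempting, and the documents do not support them.
- A reader might take the stated goal to "assess the impact of adjunctive US-guided DOT on the accuracy of breast biopsy recommendations" as making accuracy the purpose of the CEM aim. That sentence is the main study goal, which Section 7 goes on to define as fewer benign biopsies with sensitivity maintained.
- A reader might say that the plan prescribes pooling over benign and malignant lesions. It does not say so. Pooling is the default reading because no stratification is stated.
- A reader might infer that comparability will be judged from kappa or McNemar, so that the alternative plan would be triggered wrongly. Section 7.1 makes no such link; the trigger is simply undefined.
- A reader might conclude that CEM results are never set against pathology. Section 7.1, Aim 1.2, plans an ad hoc review of CEM and histopathologic features in false-negative cases, although that does not compare the modalities.

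It is also fair to say that the examples are constructed. All disagreements run one way, full cancellation needs a particular ratio of gains, and if one modality simply calls more lesions positive in both groups the counts add rather than cancel.

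**Conclusion.** The point holds as a limited one. As written, the analyses of Aim 1.4 can describe agreement between DOT and CEM but cannot show which is more accurate. McNemar over all lesions can show little or no difference when one modality is better in both groups. The extent depends on quantities that the documents do not give: near the cancelling ratio the overall test has almost no power (about 3% at the assumed sizes), while away from it the loss is partial (21% against 37% for benign lesions alone in the milder scenario). That kappa is blind to direction needs no special case.

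The aim is exploratory, with no level, power or success criterion attached to it. No primary or secondary conclusion is affected, so this is an inexpensive improvement and not a flaw in the trial's main analysis.

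**What to change.** In Section 10.4, for the CEM subset:
1. Keep kappa and the tHb–enhancement correlation, labelled as descriptions of agreement.
2. Add the paired difference between CI&DOT and CI&CEM in specificity among pathology-benign lesions and in sensitivity among pathology-malignant lesions, each with exact McNemar and a paired confidence interval.
3. Apply the Section 7 cut (BI-RADS 2–3 negative, 4A–5 positive) to CI&CEM, since it is now stated for CI&DOT only.
4. State how the three reads per case are used: either a separate analysis for each reader, or one analysis of all reads with clustering by patient. The reads should not be counted as independent lesions.

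In Section 7.1, Aim 1.4, say that comparability will be judged from these two differences, and state the criterion in advance.

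The change needs no new data, because the CEM assessments and biopsy results are already collected and exported together. It does need the cut and the read rule to be written down. Each pathology group is smaller than the whole subset, so intervals will be wider and tests within a group may have low power, which is acceptable for an exploratory aim.
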